8.1.1.1 Rescreening of Subjects

Subjects who screen failed may be rescreened twice. The first rescreening must be at least 2 weeks after initial screen failure. If the subject also fails on the second attempt (first rescreening), another screening attempt is allowed but must be at least 6 months after the first rescreening. All Screening procedures described in Section 8.1.1 will be repeated. If a subject screen fails three times, they are no longer eligible to be screened again.

Subjects who Run-in failed may be rescreened once, earliest after 3 months from the date of Run-in failure. All screening procedures described in Section 8.1.1 will be repeated.

Subjects can be screened maximum three times in total as shown in Table 4.

Table 4 Rescreening of Subjects

Scenario #	1st Screen	2nd Screen	3rd Screen
1	Screen Fail	Screen Fail	
2	Screen Fail	Run-in Fail	
3	Screen Fail	Randomized	
4	Run-in Fail	Screen Fail	
5	Run-in Fail	Run-in Fail	
6	Run-in Fail	Randomized	
7	Screen Fail	Screen Fail	Screen Fail
8	Screen Fail	Screen Fail	Run-in Fail
9	Screen Fail	Screen Fail	Randomized
10	Screen Fail	Run-in Fail	Screen Fail
11	Screen Fail	Run-in Fail	Run-in Fail
12	Screen Fail	Run-in Fail	Randomized

8.1.2 Run-in Phase (Single-Blinded) Procedures

The purpose of the Run-in Phase is intended for the management of serum K⁺ with patiromer (see Section 6.7.1.1) to allow optimization of ACEi/ARB/ARNi and MRA as tolerated (see Section 6.7.2). The frequency of subject weekly visits during the Run-in Phase is at the discretion of the Investigator.

Subjects with 2 Screening K⁺ values >5.0 mEq/L are considered hyperkalemic; these patients begin patiromer (single-blinded) when they qualify for the Run-in Phase (i.e., on the same day Run-in qualification is met or the next day).

All other subjects are considered normokalemic and serum K⁺ will be measured again latest at 1 week during the Run-in Phase. Patiromer will be started at the first week during the Run-in Phase only if subjects are still normokalemic or have progressed to hyperkalemia; in case of newly observed hypokalemia during the first week of the Run-in Phase, patiromer must not be given.

In subjects with hypokalemia serum K⁺ must be controlled after 3 days to evaluate the effects of up-titrated ACEi/ARB/ARNi and/or MRA. Note: Depending on the actual local serum K⁺ value this could include patiromer 0 g/day (i.e., 0 packets/day) during the Run-in Phase.

Except where noted, the following activities will be performed during all visits during the Run-in Phase:

- IWRS entry
- Measure resting heart rate (pulse) after the subject has been sitting quietly for 5 minutes
- Measure blood pressure after the subject has been sitting quietly for 5 minutes (see Section 9.3.2)
- Measure weight
- Collect blood samples for evaluation of:
 - K⁺ level (measured locally)
- Review local laboratory K⁺ results and adjust study medications according to Section 6.7.1.1
 - Magnesium level (measured locally) starting at 1 week after initiating the use of patiromer; consider periodic measurements of serum magnesium levels based on your clinical assessment of clinical signs of hypomagnesemia
 - Serum creatinine, eGFR (measured locally)
- Collect and measure urine albumin-to-creatinine ratio (ACR) (at first week during Run-in Phase only, not assessed at other Run-in Phase Visits; see Section 9.6)
- Assess AEs/special situations
- Assess ACEi/ARB/ARNi and MRA doses and determine if titration is needed (see Section 6.7.2)
- Record concomitant medications and procedures
- Investigational Pharmacist or qualified designee as assigned by the Principal Investigator performs the following:
 - Perform drug accountability
 - Dispense patiromer based on kit number(s) assigned by IWRS, if needed

- Reimburse MRA (only for subjects who are initiating spironolactone or eplerenone; see Section 6.7.2 and Section 6.8.2) if needed
- Assess if subject meets randomization criteria; if yes, the visit becomes the Day 1/Baseline Visit; see Section 8.2
- For subjects who Run-in fail a follow-up (K⁺ assessment) visit needs to be completed; see Section 8.6

8.2 Treatment Phase (Double-Blinded) Procedures

Subjects who meet all randomization criteria (see Section 5.4) within the 12 weeks of the Run-in Phase (single-blinded) may be randomized on the same day in which they qualify, and all assessments performed at the visit in the Run-in Phase when they qualified will be considered the Baseline assessments and will not be repeated. The qualifying Run-in Phase visit will become the Day 1/Baseline Visit.

If a subject cannot be randomized on the same day the randomization criteria were met, then the subject should be randomized within 1 week and all assessments described in Section 8.2.1 will be repeated on the day of randomization.

8.2.1 Day 1/Baseline Visit

The following activities will be performed at the Day 1/Baseline Visit:

- Confirm subject meets all randomization criteria
- IWRS randomization to patiromer or placebo (assignment blinded)
- Perform KCCQ and EQ-5D-5L questionnaire (see Section 9.7)
- Assess NYHA class
- Measure resting heart rate (pulse) after the subject has been sitting quietly for 5 minutes
- Measure blood pressure after the subject has been sitting quietly for 5 minutes (see Section 9.3.2)
- Measure weight
- Collect blood samples for evaluation of (see Table 5):
 - K⁺ level (measured locally and by central laboratory)
 - Serum chemistry including creatinine, eGFR (central laboratory)
 - MRA level (see Section 9.2.1)

- High sensitivity troponin
- Collect urine samples for the evaluation of
 - Urinalysis
 - Urine or serum pregnancy test
- Dispense urine sample containers for Day 3 Visit and provide proper training/instructions on use (see Section 9.6)
- Assess AEs/special situations
- Record concomitant medications and procedures
- Investigational Pharmacist or qualified designee as assigned by the Principal Investigator performs the following:
 - Perform drug accountability
 - Dispense patiromer/placebo based on kit number(s) assigned by IWRS and collect all packets or kits dispensed during the Run-in Phase

8.2.2 Day 3 Visit (± 1 Day)

The following activities will be performed at the Day 3 Visit:

- IWRS entry
- Measure resting heart rate (pulse) after the subject has been sitting quietly for 5 minutes
- Measure blood pressure after the subject has been sitting quietly for 5 minutes (see Section 9.3.2)
- Measure weight
- Collect blood samples for evaluation of:
 - K^+ level (measured locally)
 - Review local K^+ results and adjust study medications according to Section 6.7.1.2
 - Serum creatinine, eGFR (measured locally)
- Collect and measure urine ACR (see Section 9.6)
- Assess AEs/special situations

- Record concomitant medications and procedures
- Investigational Pharmacist or qualified designee as assigned by the Principal Investigator performs the following:
 - Perform drug accountability
 - Dispense patiromer/placebo based on kit number(s) assigned by IWRS as needed
- Reimburse MRA (only for subjects who are initiating spironolactone or eplerenone; see Section 6.7.2 and Section 6.8.2) if needed

8.2.3 Week 1 Visit (± 3 Days)

The following activities will be performed at the Week 1 Visit:

- IWRS entry
- Measure resting heart rate (pulse) after the subject has been sitting quietly for 5 minutes
- Measure blood pressure after the subject has been sitting quietly for 5 minutes (see Section 9.3.2)
- Measure weight
- Collect blood samples for evaluation of (see Table 5):
 - K^+ level (measured locally)
 - Review K^+ results and adjust study medications according to Section 6.7.1.2
 - Serum creatinine, eGFR (measured locally)
 - MRA level (see Section 9.2.1)
- Dispense urine sample containers and provide proper training/instructions on use (see Section 9.6)
- Assess AEs/special situations
- Record concomitant medications and procedures
- Investigational Pharmacist or qualified designee as assigned by the Principal Investigator performs the following:
 - Perform drug accountability
 - Dispense patiromer/placebo based on kit number(s) assigned by IWRS as needed

- Reimburse MRA (only for subjects who are initiating spironolactone or eplerenone; see Section 6.7.2 and Section 6.8.2) if needed

8.2.4 Week 2 Visit (± 3 Days)

If at Week 2 there are changes to ACEi, ARB, ARNi and/or MRA dose or serum K⁺ varies outside the intended range, unscheduled weekly visits should occur until stability (i.e., at 2 consecutive visits) returns.

The following activities will be performed at the Week 2 Visit:

- IWRS entry
- Measure resting heart rate (pulse) after the subject has been sitting quietly for 5 minutes
- Measure blood pressure after the subject has been sitting quietly for 5 minutes (see Section 9.3.2)
- Measure weight
- Collect blood samples for evaluation of:
 - K⁺ level (measured locally)
 - Review K⁺ results and adjust study medications according to Section 6.7.1.2
 - Serum creatinine, eGFR (measured locally)
- Collect and measure urine ACR (see Section 9.6)
- Assess AEs/special situations
- Record concomitant medications and procedures
- Investigational Pharmacist or qualified designee as assigned by the Principal Investigator performs the following:
 - Perform drug accountability
 - Dispense patiromer/placebo based on kit number(s) assigned by IWRS as needed
- Reimburse MRA (only for subjects who are initiating spironolactone or eplerenone; see Section 6.7.2 and Section 6.8.2) if needed

8.2.5 Week 6 Visit (± 14 Days)

If there are changes to ACEi, ARB, ARNi and/or MRA dose or serum K⁺ varies outside the intended range, unscheduled weekly or monthly visits should occur until stability (i.e., at 2 consecutive visits) returns.

The following activities will be performed at the Week 6 Visit:

- IWRs entry
- Measure resting heart rate (pulse) after the subject has been sitting quietly for 5 minutes
- Measure blood pressure after the subject has been sitting quietly for 5 minutes (see Section 9.3.2)
- Measure weight
- Collect blood samples for evaluation of:
 - K⁺ level (measured locally)
 - Review K⁺ results and adjust study medications according to Section 6.7.1.2
 - Serum creatinine, eGFR (measured locally)
- Dispense urine sample containers and provide proper training/instructions on use (Week 10 Visit only; see Section 9.6)
- Assess AEs/special situations
- Record concomitant medications and procedures
- Investigational Pharmacist or qualified designee as assigned by the Principal Investigator performs the following:
 - Perform drug accountability
 - Dispense patiromer/placebo based on kit number(s) assigned by IWRs as needed
- Reimburse MRA (only for subjects who are initiating spironolactone or eplerenone; see Section 6.7.2 and Section 6.8.2) if needed

8.2.6 Week 18 Visit (-30 Days) and Every 3 Months Visit Until Event-Driven EoS (-30 Days)

The following activities will be performed at the Week 18 Visit (i.e., first of the Every 3 Months visits) and at each subsequent visit that will occur every 3 months until the EoS:

- IWRS entry
- Perform KCCQ and EQ-5D-5L questionnaire at 3 (i.e., Week 18), 6, and 12 months and every 12 months thereafter (see Section 9.7)
- Assess NYHA class
- Measure resting heart rate (pulse) after the subject has been sitting quietly for 5 minutes
- Measure blood pressure after the subject has been sitting quietly for 5 minutes (see Section 9.3.2)
- Measure weight
- Collect blood samples for evaluation of (see Table 5):
 - K^+ level (measured locally and by central laboratory)
 - Review K^+ results and adjust study medications according to Section 6.7.1.2
 - Serum chemistry including creatinine, eGFR (central laboratory)
 - Hematology (central laboratory)
 - BNP or NT-proBNP (central laboratory)
 - MRA level at 3 (i.e., Week 18), 6, and 12 months and every 12 months thereafter (see Section 9.2.1)
- Collect and measure urine ACR (see Section 9.6)
- Dispense urine sample containers (see Section 9.6)
- Assess AEs/special situations
- Record concomitant medications and procedures
- Investigational Pharmacist or qualified designee as assigned by the Principal Investigator performs the following:
 - Perform drug accountability
 - Dispense patiromer/placebo based on kit number(s) assigned by IWRS as needed
- Reimburse MRA (only for subjects who are initiating spironolactone or eplerenone; see Section 6.7.2 and Section 6.8.2) if needed.

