a. For BNP and NT-proBNP inclusion criteria in relation to the presence or not of hospitalization for HF within 12 months and the presence or not of atrial fibrillation when blood samples were collected see Section 5.2.

b. Hyperkalemia or normokalemia defined by 2 local serum K^+ values each obtained from a separate venipuncture, e.g., one in each arm. If 1 serum potassium value is hyperkalemic ($>5.0 \text{ mEq/L}$) and 1 value is normokalemic ($\leq 5.0 \text{ mEq/L}$), then a third peripheral venipuncture is performed within 1 day to obtain clarity whether a subject is hyperkalemic or normokalemic.

c. Start at 8.4 g/day and up-titrate as necessary up to 25.2 g/day. Hyperkalemic subjects start patiromer immediately; normokalemic subjects start at Week 1 or later. Subject must return within 1 week (3 days) after patiromer initiation or dose adjustments to assess potassium levels.

d. Initiate/optimize selected MRA; up-titrate to 50 mg/day. For subjects not on an MRA, the Investigator determines which MRA to initiate, and also determines the starting dose. For subjects who are on $<50 \text{ mg/day}$ of MRA, double their current dose up to 50 mg/day. Assess tolerance to the 50 mg target dose

e. If there are changes to ACEi, ARB, ARNi and/or MRA dose or serum potassium varies outside the intended range, unscheduled weekly or monthly visits should occur until stability returns.

f. If the Potassium Assessment Visit is at 2 weeks after the EoS Visit, then Follow-up phone call is not required.

SCHEDULE OF EVENTS

Procedures	Screening Phase	Run-in Phase (Single-Blinded)	Treatment Phase (Double-Blinded)										U Visit ⁽⁵⁾
	Screening Visits ⁽¹⁾	Run-in Visits ⁽²⁾ (Up To 12 wks)	Day 1/ Baseline	Day 3 (±1 D)	Week 1 (±3 D)	Week 2 (±3 D)	Week 6 (±14 D)	Week 18 (-30 D), First Every 3 Months Visit	Every 3 Months Visits After Week 18 Until EoS (-30 D)	EoS/ET Visit	PA Visit ⁽³⁾ (Up to 2 Wks)	Follow-up Phone Call (at Least 2 Wks After EoS) ⁽⁴⁾	
Informed consent	X												
IWRS entry	X	X	X	X	X	X	X	X	X	X	X	X	X ⁽²⁴⁾
Eligibility criteria	X	X ⁽⁶⁾	X ⁽⁶⁾										
Demographics	X												
NYHA class	X							X	X	X	X		
Medical/surgical history	X												
Physical examination	X									X			X ⁽⁷⁾
Height	X												
Weight	X	X	X	X	X	X	X	X	X	X	X		X
BP and heart rate	X	X	X	X	X	X	X	X	X	X	X		X
12-lead ECG ⁽²²⁾	X												
K ⁽⁸⁾	L ⁽⁹⁾	L	L&C	L	L	L	L	L&C	L&C	L&C	L&C		L
Serum chemistry	L ⁽¹⁰⁾ &C ⁽¹¹⁾	L ^(12,13)	C	L ⁽¹³⁾	L ⁽¹³⁾	L ⁽¹³⁾	L ⁽¹³⁾	C	C	C	C		L

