Randomized subjects will begin their assigned treatment (patiromer or placebo) using the same number of packets established for patiromer at the end of the Run-in Phase and will continue the ACEi/ARB/ARNi and MRA regimen being administered at the end of the Run-in Phase.

Anytime during the Treatment Phase when subjects are on less than the target dose of either ACEi/ARB/ARNi or MRA, up-titration should be attempted if serum K^+ remains in the normokalemic range (serum $K^+ \geq 4.0 - \leq 5.0$ mEq/L) and no other contravening conditions are present.

After randomization, serum K^+ will be measured prior to initiation of assigned patiromer/placebo, double-blinded, on Treatment Day 1/Baseline (if not already obtained that day), and at each subsequent scheduled and unscheduled visit during the Treatment Phase. See Table 1 for the allowed interventions for the management of hyperkalemia during the Treatment Phase.

Table 1 Protocol Allowed Interventions for the Management of Hyperkalemia During the Blinded Treatment Phase

-
1. Up-titration of patiromer/placebo if on <3 packets per day
 2. Down-titration or discontinuation of ACEi, ARB, ARNi and/or MRA
 3. Initiate or increase diuretics
 4. Dietary K^+ restriction

Notes: ACEi=Angiotensin-converting enzyme inhibitor; ARB=Angiotensin II receptor blocker; ARNi=Angiotensin receptor/neprilysin inhibitor; K^+ =Potassium; MRA=Mineralocorticoid receptor antagonist.

If local K^+ is >5.5 mEq/L, one or more of these interventions must be initiated either individually or in combination following the recommendations by practice guidelines. Repeat the K^+ measurement within 7 days; if local K^+ remains >5.5 mEq/L consider repeating the intervention or using other interventions in the order presented in Table 1.

If local K^+ is between >5.0 mEq/L and 5.5 mEq/L, one or more of these interventions may be initiated per Investigator discretion.

Urgent treatment of hyperkalemia should be in accordance with usual care and the Investigator's judgment. As described in Section 6.8.4.1, the only K^+ binding medications permitted for use during the study are temporary use of sodium or calcium polystyrene sulfonate as well as sodium zirconium cyclosilicate for up to 7 days or until local serum K^+

<5.0 mEq/L, whichever occurs first. Patiromer/placebo must be withheld during temporary use of permitted K⁺ binding medications.

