6.7.4 Management of eGFR Level

Throughout the treatment period, creatinine will be measured at each study visit (and may be measured at Unscheduled Visits). Subjects should be monitored for changes in renal function, especially during periods of medication changes or adjustments. Acute reductions in glomerular filtration rate have been seen with the initiation of MRA, similar to those seen with initiation of ACEi and ARB that have been attributed to transient changes in glomerular hemodynamics [31,32]. These changes typically do not impact long-term renal function. In this study, use of the Kidney Disease Outcomes Quality Initiative (KDOQI) recommendations for the detection and management of decreases in eGFR when initiating or up-titrating ACEi/ARB/ARNi or MRA [33] should be considered.

Based on KDOQI guidelines:

- An early decline in eGFR is defined as >15% reduction from Baseline (Screening) within 4 weeks of initiation of ACEi/ARB/ARNi or MRA.
- For decreases in eGFR up to 30%, no changes to ACEi/ARB/ARNi or MRA dosing need to be made, and eGFR may be followed routinely.
- Decreases in eGFR >30%, however, should prompt a search for other etiologies of abrupt renal function decline, including prerenal and postrenal causes, toxic reactions, and renal artery disease.
- For a decline in eGFR from $\geq 31\text{--}50\%$, the ACEi/ARB/ARNi or MRA dose should be decreased and the eGFR followed weekly. If the eGFR does not return to within 30% of Baseline within 4 weeks, ACEi/ARB/ARNi or MRA should be discontinued.
- ACEi/ARB/ARNi or MRA should be discontinued for a decline in eGFR >50% and eGFR should be followed at least weekly until eGFR has returned to within 15% of the Baseline value, and biweekly thereafter until stabilized.
- An eGFR decline >50% must be reported as an AE; see Section 10.5 for reporting of AEs.

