8.3 Unscheduled Visit Procedures

An unscheduled visit may occur at the discretion of the Investigator.

During the Double-Blinded Treatment Period, anytime there are changes to ACEi, ARB, ARNi and/or MRA dose or interventions for serum K⁺ outside the desired range, additional Unscheduled Visits should occur weekly until the ACEi, ARB, ARNi and/or MRA dose or serum K⁺ has been stable for at least 2 consecutive visits.

At an unscheduled visit during any phase of the study, the following activities will be performed:

- IWRS entry, in case IMP is to be re-dispensed
- Measure resting heart rate (pulse) after the subject has been sitting quietly for 5 minutes
- Measure blood pressure after the subject has been sitting quietly for 5 minutes (see Section 9.3.2)
- Measure weight
- Collect blood samples for evaluation of:
 - K⁺ level (measured locally)
 - Serum creatinine, eGFR (measured locally)
- Assess AEs/special situations
- Record concomitant medications and procedures

Any other study assessments (see Section 8.8) may be performed at the discretion of the Investigator during an unscheduled visit.

The following activities are optional during an unscheduled visit:

- Perform physical examination
- Collect blood sample for the evaluation of hematology (central laboratory)
- Investigational Pharmacist or qualified designee as assigned by the Principal Investigator performs the following:
 - Perform drug accountability
 - Dispense patiromer/placebo based on kit number(s) assigned by IWRS

- Reimburse MRA (only for subjects who are initiating spironolactone or eplerenone; see Section 6.7.2 and Section 6.8.2) if needed

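### Protocol 8.2.5 permits monthly unscheduled visits after an ACEi/ARB/ARNi or MRA dose change, where the synopsis, 4.1, 8.2.4 and 8.3 ask for weekly visits

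*Protocol*

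**What the plan says.** Protocol 8.3, the section on unscheduled visits, sets the general rule. Its trigger is "During the Double-Blinded Treatment Period, anytime there are changes to ACEi, ARB, ARNi and/or MRA dose", or an intervention for K+ outside the desired range. Its frequency is "additional Unscheduled Visits should occur weekly until the ACEi, ARB, ARNi and/or MRA dose" or K+ has been stable for at least two consecutive visits. The synopsis (Procedures) and 4.1 give the same rule for the Treatment Period.

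Two visit sections add their own sentence. For a change at Week 2, 8.2.4 says "unscheduled weekly visits should occur until stability (i.e., at 2 consecutive visits) returns". For Week 6, 8.2.5 says "unscheduled weekly or monthly visits should occur until stability (i.e., at 2 consecutive visits) returns". Section 8.2.6 (Week 18 onward) has no such sentence.

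Note e to the Study Schema says "unscheduled weekly or monthly visits should occur until stability returns". The figure is not shown in the text available for review, so the point where the note attaches cannot be seen.

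**The concern.** The same event, a change in ACEi/ARB/ARNi or MRA dose during the Treatment Phase, carries two follow-up frequencies. A site that reads 8.2.5 alone may wait a month before the first recheck of K+ and creatinine, while a site that reads 8.3 rechecks after a week. No criterion is given for choosing.

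The frequency matters most after Week 6, because the next scheduled visit is Week 18. Until then, unscheduled visits are the protocol's specified route to these laboratory checks after a dose change; 8.3 lists K+ and creatinine/eGFR at each one. Dose changes are expected in this period, since 4.1 says "Anytime during the Treatment Phase when subjects are on less than the target dose of either ACEi/ARB/ARNi or MRA, up-titration should be attempted" when K+ is 4.0 to 5.0 mEq/L and nothing else stands against it. At stake is timely detection of a K+ rise or a fall in renal function in individual patients.

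**Working it through.** **Step 1. The passages side by side.** All are current text.

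| Place | When it applies | Trigger | Frequency |
|---|---|---|---|
| Synopsis, 4.1, 8.3 | Any time in the Treatment Phase | Dose change, or K+ intervention | Weekly |
| 8.2.4 | Week 2 | Dose change, or K+ out of range | Weekly |
| 8.2.5 | Week 6 | Dose change, or K+ out of range | Weekly or monthly |
| Schema note e | Not shown | Dose change, or K+ out of range | Weekly or monthly |
| 8.2.6 | Week 18 onward | No sentence | 8.3 applies |

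The dose-change trigger is the only one common to every passage that states a frequency. The general rule covers any time in the Treatment Phase, so it includes Week 6, and the conflict at 8.2.5 is direct. Taken together, the rules run weekly at Week 2, weekly or monthly at Week 6, and weekly again from Week 18. That looks more like an oversight than a planned relaxation. Section 8.2.5 also still carries an instruction for a Week 10 visit, which the schedule does not contain. This suggests, without proving, that the section was not fully updated.

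**Step 2. Cases already covered by another rule.**

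- Local K+ above 5.5 mEq/L: repeat K+ within 7 days (synopsis, 4.1, 6.7.1.2).
- eGFR fall of 31 to 50%: "the ACEi/ARB/ARNi or MRA dose should be decreased and the eGFR followed weekly". Above 50%: at least weekly (6.7.4).
- Any medication change: the synopsis makes monitoring of eGFR and creatinine obligatory, but names no interval.

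What remains is mainly a dose change at K+ of 5.5 or below without an eGFR fall above 30%. Examples are an ACEi/ARB/ARNi increase from the 50% of target that suffices for randomization (5.4), return to the MRA target dose after an earlier reduction, or a discretionary reduction at K+ above 5.0 and up to 5.5.

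**Step 3. Size in the remaining case.** Assumption: one month is 30.4 days, range 28 to 31.

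- First recheck, weekly: 7/7 = 1 week.
- First recheck, monthly: 30.4/7 = 4.3 weeks (28/7 = 4.0; 31/7 = 4.4).
- Two consecutive visits, weekly: 2 × 7/7 = 2 weeks.
- Two consecutive visits, monthly: 2 × 30.4/7 = 8.7 weeks (56/7 = 8.0; 62/7 = 8.9).

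These are upper limits, because monthly visits are permitted and not required.

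**Step 4. Next scheduled visit.** Nominally 18 − 6 = 12 weeks later. With the visit windows (Week 6 ± 14 days; Week 18 up to 30 days early), the shortest gap is (126 − 30) − (42 + 14) = 40 days, or 5.7 weeks. The longest is 126 − (42 − 14) = 98 days, or 14 weeks. Even the shortest gap exceeds one month.

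**The case against.** The strongest reply is that the texts can be read together. The trigger in 8.2.5 includes K+ outside the intended range whether or not anyone intervenes, and intervention is optional at K+ above 5.0 and up to 5.5. The monthly option could be meant for that untreated case, with 8.3 settling every dose change. This is sensible as policy, but 8.2.5 does not say it: one sentence attaches both frequencies to both triggers. A clarifying edit is still needed.

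Several limits on the point stand. All the unscheduled-visit sentences are recommendations. Weekly visits satisfy every passage, and the Investigator may call a visit at any time (6.7.1.2). The safeguards in step 2 remove the most dangerous situations for the parameter each covers. MRA up-titration in the Treatment Phase arises only after an earlier reduction, because randomization requires at least the target dose. The Study Manual is not available, so a rule there cannot be excluded, although none of these passages refers to it for visit frequency. Because the position of note e is unknown, it cannot be counted as an independent second conflict.

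A reader might also infer that monthly visits would undercut the discontinuation decision in 6.7.4, which turns on "If the eGFR does not return to within 30% of Baseline within 4 weeks". The documents do not support that. The decision arises after an eGFR fall of 31 to 50%, and for exactly that case 6.7.4 itself calls for weekly eGFR follow-up.

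**Conclusion.** The inconsistency is real at 8.2.5 and minor. In the narrow case left by the other safeguards, the first recheck of K+ and creatinine could move from 1 week to about 4.3 weeks (4.0 to 4.4). This rests on the assumed length of a month and on a site choosing the monthly option; the documents do not say whether any site did.

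A reader might infer a distortion of the first key secondary endpoint, time to first K+ above 5.5 mEq/L, because SAP 2.13 lets time-to-event analyses use unscheduled values. The documents do not support a claim of bias: the same wording applies in both blinded arms, and nothing shows that monthly visits were used, or used more in one arm. The primary analysis by visit is little affected, since SAP 2.13 bases summaries by visit on scheduled visits.

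Confidence in the text comparison is high. The clinical consequence is possible but not demonstrated. The prospective gain is small: version 4.0 is dated 23 June 2021, and SAP 2.2 records that sites were told of closure on June 24, 2021.

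**What to change.** In 8.2.5, remove the monthly option for ACEi/ARB/ARNi or MRA dose changes and for K+ interventions. State that unscheduled visits are weekly until the subject is stable at two consecutive visits, and refer to 8.3. Make the same edit in Study Schema note e for consistency. If monthly visits are wanted for untreated K+ above 5.0 and up to 5.5 mEq/L, say so in a separate sentence limited to that case.

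The cost is a one-sentence edit in two places and a short note to sites with subjects still on treatment. No SAP change is needed. The downside is a few more unscheduled visits at sites that would have chosen monthly, and 8.3 already calls for those visits. A subject who is stable at once needs two visits under either frequency.
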